To determine the clinical acceptability of the restoration they are evaluated scoring for their esthetic, functional and biologic properties, which are shown in Table 1. The test requires a sharp explorer plus visual inspection, aided by a mouth mirror as needed. A photographic record will be made of each restoration. For evaluation of marginal adaptation a set of

explorers with different blunt tips of 50, 150 and 250 μm is recommended by Hickel et al. [16]. For assessment of contact point metal strips of different thicknesses of 25 μm , 50 μm and 100 μm can be used. The explorers and metal strips will be provided by the sponsor.

The two masked examiners will use a two-step approach for assigning scores for each parameter. The first step is to assess the restoration and to determine the level of clinical acceptability for each parameter in each of the categories. The result becomes unacceptable whenever re-treatment is necessary.

If a parameter is judged to be acceptable, as a second step, a further distinction can be made between an excellent, good, or clinically satisfactory result. Score 1 means that the quality of the restoration is excellent and fulfils all quality criteria and the tooth and/or surrounding tissues are adequately protected. Score 2 should be selected when the quality of the restoration is still highly acceptable, although one or more criteria deviate from the ideal. The restoration could be modified by polishing and upgraded to an “excellent” rating, but this is not normally necessary. There is no risk of damage to the tooth and/or surrounding tissue. Score 3 means that the quality of the restoration is sufficiently acceptable but with minor shortcomings. Because of their location/extent, however these cannot be eliminated without damage to the tooth, although no adverse effects are anticipated. Scores 1 and 2 would correspond to Ryge’s Alfa rating; Score 3 is equivalent to Bravo.

If a parameter is judged to be unacceptable, a further distinction can be made between a clinically unsatisfactory and clinically poor result. Scores 4 and 5 correspond to Ryge’s Charlie and Delta scoring, which means that a restoration scored 4 is unacceptable but repairable whereas a restoration scored 5 must be replaced [16].

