In the event of a restoration being considered to be clinically unsatisfactory, this restoration will be excluded from the study and arrangements made to replace or, if appropriate, repair the defective or failed restoration. The mode of failure of the restoration will be documented (Failed Restoration Form).

The examiners assigned to review the restorations will have been trained in the evaluation system to be used, and will be capable of achieving at least 85% reproducibility in their assessments.

The reviews will take place at one, two, three, and five years \pm 1 month after placement.

Adverse events or adverse device effects

The Investigators are responsible for identifying adverse events, any untoward medical occurrence, that occurs to each subject throughout the study. Adverse events must be documented on the (Serious) Adverse Event Form (Appendix 2). Serious adverse events must be reported to the Sponsor within 24 h. Study subjects who have experienced an adverse event may remain in the study as long as the safety, rights and /or welfare of subjects

are not put at risk and/or the restoration is unaffected concerning its quality and function. Serious adverse events are adverse events that (a) led to a death; (b) led to a serious deterioration in the health of the subject, or (c) led to fetal distress, fetal death or a congenital abnormality or birth defect.

A device-related adverse event is one considered by the investigator to have a reasonable likelihood of being associated with the investigational device and is called an adverse device effect. Adverse device effects must be documented on the Adverse Device Effect Form. Serious adverse device effects must be reported within 24 h to the contact person at **3M ESPE, [contact]**. A serious adverse device effect is an effect that resulted in any of the consequences characteristic of a serious adverse event.

(Near) Incident is any malfunction or deterioration in the characteristics and/or performance of a device, as well as any inadequacy in the labelling or instruction for use, which might lead or might have led to the death of a patient or user or to a serious deterioration in his state of health.

Any incident that led to any hazard for the patient has to be regarded as adverse device effect and documented accordingly. The Investigator reports serious (near) incidents as soon as possible and no later than 24 h to 3M ESPE.

SUBJECT INCENTIVES

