3. Clinically sufficient / satisfactory (minor shortcomings, no unacceptable effects but not adjustable without damage to the tooth)	5.3. Two or more or larger hairline cracks and / or chipping (not affecting the marginal integrity or proximal contact).	6.3.1. Gap < 150 µm not removable. 6.3.2. Several small enamel or dentin fractures.	7.3. Differing wear rate to enamel but within the biological variation (< 50 % or 150-300 % of corresponding enamel).	8.3. Slightly too weak, no indication of damage to tooth, gingiva or periodontal structures (50 µm metal blade can pass easily but not 100 µm).	9.3. 1. Marginal gap < 200 µm. 9.3. 2. Negative steps visible < 250 µm. No adverse effects noticed. 9.3.3. Poor radiopacity of filling material.	10.3. Minor criticism of aesthetics. 10.3.1. Aesthetic shortcomings. 10.3.2. Some lack of chewing comfort. 10.3.3. Time consuming procedure and / or similar. No adverse clinical effects.
4. Clinically unsatisfactory (but repairable)	5.4. Chipping that damage marginal quality or proximal contacts, bulk	6.4.1. Gap > 250 µm or dentin / base exposed.	7.4. Wear considerably exceeds normal enamel wear, or occlusal contact	8.4. Too weak (100 µm metal blade can pass) and possible damage (food	9.4.1. Marginal gap > 250 µm. 9.4.2. Excess accessible but not removable.	10.4. Desire for improvement (reshaping of anatomic

	fractures with or without partial loss (less than half of the restoration).	6.4.2. Chipping damaging margins. 6.4.3. Notable enamel or dentin wall fracture.	points are lost (restoration > 300 % of enamel wear or antagonist > 300 %).	impaction). Repair possible.	9.4.3. Negative steps > 250 µm and repairable.	form or refurbishing, etc.).
5. Clinically poor (replacement necessary)	5.5. (Partial or complete) loss of restoration.	6.5. Filling is loose but in situ.	7.5. Wear is excessive (restoration or antagonist > 500 % of corresponding enamel).	8.5. Too weak and / or clear damage (food impaction) and / or pain / gingivitis. Requires replacement.	9.5.1. Secondary caries, large gaps. 9.5.2. Apical pathology. 9.5.3. Fracture / loss of restoration or tooth.	10.5. Completely dissatisfied and / or adverse effects including pain.

c) Biological properties	11. Postoperative (hyper) sensitivity and tooth vitality	12. Recurrence of caries, erosion, abfraction	13. Tooth integrity (enamel cracks)	14. Periodontal response (always compared to a reference tooth)	15. Adjacent mucosa	16. Oral and general health

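### Does the unscored 150–250 µm range in the marginal adaptation criterion (Table 1, criterion 6) leave the failure call undefined?

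*Combined protocol and SAP*

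**What the plan says.** The primary endpoint is the clinical rating of the restorations on the scale in Table 1, where scores 1 to 3 are acceptable and 4 and 5 are not. For criterion 6, in part b) Functional properties, the descriptors at this line are:

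- Score 3: "6.3.1. Gap < 150" µm and not removable, or several small enamel or dentin fractures.
- Score 4: "6.4.1. Gap > 250" µm or exposed dentin or base; or margin-damaging chipping; or a notable wall fracture.
- Score 5: "6.5. Filling is loose but in situ", with no width attached.

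For marginal adaptation, the Follow-up Assessment section recommends a set of "explorers with different blunt tips of 50, 150 and 250" µm, which the sponsor supplies. What it requires is a sharp explorer and visual inspection.

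The same section sets a two-step procedure. Step one settles acceptability: "The result becomes unacceptable whenever re-treatment is necessary". Step two chooses the score within the acceptable or unacceptable group. Score 3 is for shortcomings such that "these cannot be eliminated without damage to the tooth, although no adverse effects are anticipated", while "a restoration scored 4 is unacceptable but repairable". If a restoration is judged clinically unsatisfactory, "this restoration will be excluded from the study" and it is repaired or replaced.

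**The concern.** The two width descriptors do not meet. If the three tips are used, one of the possible readings (the 150 µm tip enters, the 250 µm tip does not) has no width-based score, and it falls between the last acceptable and the first unacceptable score. Elsewhere in the table, numbers on the two sides of this line do meet: wear at 300 %, contact point at the 100 µm blade, radiographic negative steps and enamel splits or cracks at 250 µm. That makes criterion 6 look like an error.

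The line matters. A call of unsatisfactory removes the restoration from follow-up, so its later scores cannot be recovered. Marginal integrity is also one of the properties named in the Hypothesis to be Tested section. If examiners called such margins differently from visit to visit, the failure counts would carry avoidable noise.

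**Working it through.** The plan states no figure on this point, so there is nothing to reproduce. The check is whether any margin is left without a score.

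**Width alone.** Inputs: the criterion 6 descriptors in Table 1 and the tips named in Follow-up Assessment.

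| Reading | Below 150 µm? | Above 250 µm? | Side of the line by width |
|---|---|---|---|
| 50 µm tip does not enter | yes | no | acceptable |
| 50 enters, 150 does not | yes | no | acceptable |
| 150 enters, 250 does not | no | no | none |
| 250 enters | no | yes | unacceptable |

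One of four readings has no width-based score, and the open band is 250 − 150 = 100 µm wide. For the radiographic marginal gap in criterion 9 (below 200 µm for score 3, above 250 µm for score 4) it is 250 − 200 = 50 µm. Criterion 13 leaves open only the single value 250 µm.

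**Width plus the rest of the plan.** Take a margin in the 150–250 µm band.

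1. If dentin or base is exposed, the margin is chipped in a damaging way, or a wall is notably fractured, it is score 4 at any width. A loose filling is score 5 at any width.
2. Otherwise step one applies. If re-treatment is needed, the margin is unacceptable, and score 4 covers the repairable case and score 5 replacement.
3. If re-treatment is not needed, the margin is acceptable, and the general description of score 3 fits a shortcoming that cannot be removed without harming the tooth.

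These branches cover every case, so no margin is left without a score. The re-treatment judgement is also the thing the scale sets out to measure. Width is one descriptor of it.

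**Is criterion 6 exceptional?** Less than it seems. Item 8.4 couples the 100 µm blade with possible damage, so a blade that passes without damage fits neither 8.3 nor 8.4. Item 9.4.3 requires the step to be repairable, so a larger step that is not repairable has no step descriptor. Within criterion 6, score 2 names the single value 50 µm while score 3 says below 150 µm, so these are not separate bins. The table works as a set of ordered descriptors applied with judgement.

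**Scale.** With 50 restorations per material (Distribution of restorations), one reclassified case moves that material's failure percentage by 1/50 = 2.0 points. With 40 per material, an assumption borrowed from the guideline minimum in Subject Population and Sample Size, it is 1/40 = 2.5 points. If the materials differed by d band cases and all were moved across the line, the difference between materials would shift by d/50 or d/40. For an assumed d of 0, 1, 2 or 3 that is 0, 2.0, 4.0 or 6.0 points, or 0, 2.5, 5.0 or 7.5 points. These are ceilings for each d, because a band case already scored 4 or 5 on another descriptor does not change the count. They say nothing about how often band gaps occur.

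**The case for a change.** The best case for a change is that it is cheap and that discretion sits exactly where the table otherwise offers a measurement. Discussion settles a disagreement about one restoration but writes down no rule to keep calls alike over reviews at one, two, three and five years. The training requirement of at least 85% reproducibility gives no width for this reading. Photographs, impressions and scans are kept, but no re-reading is planned and nothing says they resolve 150–250 µm. Noise is also not wholly harmless here: scoring error unrelated to material tends to shrink a true difference, and the trial's hypothesis is one of similarity.

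The textual gap stands, and so does the point that nobody has written down how a band reading is scored. The need for an amendment does not. The examiners are masked and work independently, and each pair supplies one restoration of each material, so there is no reason for the discretion to favour either side. The 85% requirement is the plan's own control on inconsistent scoring. The tips are recommended, not required, so the four-reading grid is one way of working within the scale and not the procedure itself.

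Changing a descriptor also has a price. Table 1 is presented as a published scale, and the Primary outcome measures section complains that repeated modification of the older criteria made studies hard to compare. Whether the open band is in the published source or is a copying slip cannot be told from these documents.

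**Conclusion.** No change to the plan is needed. Table 1 leaves 150–250 µm without a width-based score in criterion 6, and 200–250 µm in the radiographic item of criterion 9. The re-treatment rule and the non-width descriptors still give every such margin a score. Followed as written, the plan produces no wrong result.

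The remaining effect is some examiner discretion at the line between scores 3 and 4, of unknown frequency and with no expected tilt toward either material. The percentage-point figures rest on assumed imbalances and are not evidence of impact.

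This conclusion assumes that masking holds and that training covers the two-step procedure. How the examiners treat a band reading is a detail that can be settled at that training and noted with the scores. The case report form is not among the documents and may already record the tip reading. Extra report tables would have no demonstrable gain.
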